## I. RESEARCH CONTEXT

Colorectal cancer, a prevalent tumor in the digestive tract, has shown an increasing incidence rate year by year. Laparoscopic right hemicolectomy serves as the standard surgical approach for tumors involving the ascending colon, cecum, and partial transverse colon, with its conventional resection scope encompassing portions of the ileum, ileocecal valve, cecum, ascending colon, and transverse colon [1]. The ileocecal valve—a semilunar fold formed by thickened muscular tissue and mucosal lining at the terminal ileum's junction with the cecum—functions as a sphincter-like structure that separates the small intestine from the large intestine. This anatomical feature plays a crucial role in regulating nutrient absorption through intestinal contents [2-3]. However, current right hemicolectomy procedures routinely omit ileocecal valve preservation, neglecting this critical physiological structure. This omission may lead to two major complications: (1) Loss of the ileocecal valve's "gate mechanism": As a bidirectional valve, the ileocecal valve restricts intestinal contents from rapidly flowing into the cecum, thereby maintaining nutrient absorption efficiency. Valve absence allows excessive intestinal contents to enter the colon, disrupting bile acid reabsorption and potentially causing both bile acid malabsorption (BAM) and bile acid diarrhea (BAD)[4]. (2) Disruption of the ileocecal valve's "anti-reflux defense": When colonic bacteria infiltrate the ileum and proximal small intestine, they compromise the intestinal microbiota barrier, triggering severe bacterial overgrowth (SIBO). This condition frequently causes recurrent abdominal bloating, diarrhea, and other chronic gastrointestinal symptoms. In severe cases, it may impair nutrient absorption including vitamin B12 and fatty acid processing – a common complication in right hemicolectomy patients that significantly compromises postoperative recovery outcomes[5].

According to the existing research, there are two ways to preserve the function of the ileocecal valve: one is to reduce the scope of surgical resection and directly retain the ileocecal valve; the other is to reconstruct the corresponding function after the removal of the ileocecal valve as far as possible. However, there are the following

problems in clinical application:

1. For patients with ileocecal valve retention, studies have reported that ileostomy with ileocecal valve preservation in ulcerative colitis can reduce high-volume fluid loss during the stoma. Additionally, solid food intake leads to firmer stools within one week after resuming solid diet post-surgery, with over 10% weight gain observed within one year. This approach also improves quality of life for patients undergoing total colectomy [10]. Current research on right hemicolectomy with ileocecal valve preservation for tumors in the hepatic flexure and transverse colon has demonstrated feasibility and surgical safety. Postoperative recovery shows significant advantages: patients in the valve-preserving group pass gas earlier and resume bowel movements sooner than non-preserved groups [11]. However, due to the extremely low incidence of hepatic flexure and transverse colon cancers (2%-4% for transverse colon, 0.7%-3% for hepatic flexure), this procedure faces practical limitations. For instance, its application to tumors in other colonic regions may result in insufficient resection margins. Consequently, many right hemicolectomy patients still face the necessity of removing the ileocecal valve along with tumor removal.

2. The concept of reconstructing the ileocecal valve was first proposed by Kellogg in 1918 [6]. Later, Itzhak Vinograd applied the concept of reintegrating the ureter into submucosal tubular valves for reconstructing the ileocecal valve, with results showing that the time for intestinal contents to pass through in the reconstructed group was significantly longer than the control group ( $16.2 \pm 1.5$ min vs  $4.1 \pm 1.0$  min), meaning the submucosal tunnel method quadrupled transit time [7]. Chardavoyn et al. employed a papillary flap technique, where a segment of the distal small intestine was grafted into the colon to form an embedded papilla approximately 4cm in diameter. To stabilize the ileocecal valve and prevent slippage, non-absorbable sutures were reinforced between the opposing serosal surfaces in a circular pattern before implantation. Postoperative analysis of intestinal microbiota revealed significantly reduced bacterial reflux in the papillary flap group compared to conventional anastomosis groups [8]. These methods have achieved satisfactory outcomes in

treating children with congenital ileocecal valve atresia and patients requiring combined resection due to non-neoplastic causes [9], indicating potential clinical benefits of ileocecal valve reconstruction. However, these approaches also present notable limitations: (1) The relatively thin colon wall makes submucosal tunnel reconstruction prone to bowel perforation; (2) The complex procedural steps hinder clinical application and promotion.

Building on these findings, this study proposes an innovative ileocolonic anastomosis approach based on the integrated reconstruction concept of mucosal folds within the ileocecal valve and the annular muscle outside the valve. The "Revolute Insert Side-End ileocecal valve reconstruction (RISE)" method combines "revolute insertion of the ileocecal valve" with "sleeve embedding reconstruction of the colonic muscle" in the ileal pouch. Preliminary small-sample clinical data demonstrate that this RISE-based ileocecal valve reconstruction technique features simple operation and a distinct "gate effect". Compared to conventional ileocolonic side-to-side anastomosis, patients with RISE anastomosis exhibit faster postoperative intestinal function recovery and significantly improved bowel function quality, highlighting the unique advantages of RISE. Notably, there was no significant difference in short-term complications between RISE and conventional anastomosis groups, indicating good surgical safety. This study plans to conduct a multicenter clinical comparative trial combining complete laparoscopic/robot-assisted right hemicolectomy with RISE anastomosis, observing its effects on short-term and long-term complication rates, quality of life, bowel function, gut microbiota, nutrient absorption, and long-term oncological outcomes.

## **II. RESEARCH OBJECTIVES**

### **1. Main objectives:**

To evaluate the efficacy of total laparoscopic/robot-assisted right hemicolectomy combined with ileocolonic RISE anastomosis (intervention) in improving postoperative stool formation time (primary outcome) in patients with right hemicolectomy for colorectal cancer compared with traditional side-to-side

anastomosis.

## **2. Secondary purposes:**

- (1) Compare the surgical safety of the two groups (RISE anastomosis group vs. traditional anastomosis group), including intraoperative bleeding, anastomotic leakage rate (Clavien-Dindo classification), and complication rate within 30 days after surgery;
- (2) To evaluate the effects of RISE anastomosis on postoperative nutritional and metabolic disorders, including serum albumin, vitamin B12, bile acid levels, and body composition analysis (body fat percentage, muscle mass);
- (3) To analyze the improvement effect of RISE anastomosis on postoperative quality of life, and evaluate it by EORTC QLQ-C30 and QLQ-CR29 scale scores;
- (4) To explore the long-term effects of RISE anastomosis on overall survival (OS) and progression-free survival (PFS);
- (5) Detect the dynamic changes of intestinal flora abundance (such as *Proteus*, *streptococcus*, obligate anaerobic bacteria, etc.) and metabolites (such as short chain fatty acids) in the two groups after surgery to clarify the regulatory effect of RISE anastomosis on intestinal microecology.

## **III. RESEARCH DESIGN**

### **1. Research on the overall design**

This prospective, single-blind, double-arm, multicenter, randomized controlled clinical trial with superiority design aims to compare postoperative intestinal function recovery between complete laparoscopic/robot-assisted right hemicolectomy combined with RISE anastomosis and traditional side-to-side anastomosis in patients with right-sided colon cancer. Eligible participants will be randomly assigned into RISE anastomosis and conventional anastomosis groups through zonal randomization, with evaluation of key outcomes including postoperative bowel function recovery (primary endpoint), complications, nutritional metabolism, quality of life, and oncological prognosis. Patients must provide informed consent prior to surgery, and all procedures are performed by senior physicians with extensive experience at each

center to ensure standardized protocols.

### **1.1 Random grouping method-block randomization**

Randomized design: Block Randomization was used, and computer-generated random sequences (SAS 9.4) were used to assign subjects to either RISE or traditional groups on a 1:1 basis.

Group setting: The size of the fixed group is 4 cases (2 cases per group) to ensure balanced number of cases between groups. The order of the groups is randomly arranged (e.g., AABB, ABAB, BAAB, etc.) to prevent prediction of the distribution pattern.

Blind assignment: The random results are sealed in an opaque envelope, which only indicates the research center and the subject enrollment number. After signing the informed consent form, the independent research assistant of the sub-center unpacks the envelope to carry out the grouping, ensuring that the assignment process is irreversible and cannot be traced back.

Implementation process:

The random sequence is generated uniformly by the statisticians of the leading unit;

The groups were assigned according to the order of case reception in the sub-center;

If the number of cases in a sub-center is less than one group (4 cases), the remaining quota will be filled according to the random sequence.

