### **1.2 Blinding-single-blind**

Blind subjects: Patients were not informed of the specific anastomosis method, and postoperative care and follow-up procedures were kept consistent to avoid inter-group exposure differences.

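### The disclosed fixed block of 4 lets anyone at a site who tracks earlier allocations know on average one third of assignments in advance, so random ordering does not fully prevent prediction

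*Protocol*

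**What the plan says.** Section III.1.1 of the protocol sets a 1:1 permuted-block scheme with one block size: "The size of the fixed group is 4 cases (2 cases per group) to ensure balanced number of cases between groups". It gives the purpose of the random order within blocks as "to prevent prediction of the distribution pattern".

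The envelopes are opaque and carry a label "which only indicates the research center and the subject enrollment number". After consent, "the independent research assistant of the sub-center unpacks the envelope to carry out the grouping". On the running order, the section says "The groups were assigned according to the order of case reception in the sub-center". For a centre with fewer than four cases, it says only that "the remaining quota will be filled according to the random sequence".

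Section III.1.2 describes the blinding: "Blind subjects: Patients were not informed of the specific anastomosis method". No one else is said to be blinded. Under section III.1, "all procedures are performed by senior physicians with extensive experience at each" centre, and the two arms in section III.4 (Treatment) are visibly different reconstructions.

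Section III.3 sets quotas of 108 for the lead centre and 20 for each of four others, 188 in all, and says they were chosen to fit the block sizes. It describes the block of 4 as a minimum, where III.1.1 calls it fixed.

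**The concern.** Random order within a block hides the start of the block but not its end. Once one arm has used both its places, the rest of the block is determined. The block size is printed in the protocol and staff who are not blinded see each operation, so someone at a centre could know the next arm before the next patient is approached.

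The envelope procedure hides what is inside the next envelope. It does not hide the previous operations, from which that content can follow. Eligibility is judged and consent signed before the envelope is opened, so foreknowledge could influence who is approached or in what order. The written eligibility criteria narrow that room without closing it. What is at stake is selection bias. The protocol gives no basis for estimating its effect on the primary endpoint, and that anyone tracks allocations is an inference.

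**Working it through.** The protocol states no predictability figure, so there is none to reproduce.

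**Inputs**
- Block of 4, two per arm, 1:1 (III.1.1).
- Quotas 108 + 4 × 20 = 188 (III.3, Table 1), which is 27 + 4 × 5 = 47 blocks.
- Assumption: the six orders of a 2:2 block are equally likely.
- Assumption: blocks are completed within each centre. The envelope labels, the running order in the sub-centre and quotas divisible by 4 support this.
- Assumption for the main figure: the observer knows every earlier allocation at the centre and where each block starts.

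**Step 1: certain assignments per block.** An assignment is certain when one arm's two places are already used. AABB and BBAA have 2 certain places each; ABAB, ABBA, BAAB and BABA have 1 each.

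(2 + 2 + 1 + 1 + 1 + 1) / (6 × 4) = 8/24 = 33.3%

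By position the chance of certainty is 0, 0, 1/3 and 1. A single block gives 25% (probability 2/3) or 50% (probability 1/3).

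**Step 2: whole trial.** The number certain is 47 + Binomial(47, 1/3).
- Mean 47 + 15.7 = 62.7; possible range 47 to 94; 5th to 95th percentile 57 to 68.
- Lead centre: 27 + 27/3 = 36 of 108 (27 to 54).
- Each other centre: 5 + 5/3 = 6.7 of 20 (5 to 10).

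**Step 3: best guess.** Always guessing the arm with more places left is right with probability 1/2, 2/3, 2/3 and 1 at the four positions: (0.5 + 0.667 + 0.667 + 1)/4 = 70.8%, against 50% with no information.

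**Step 4: partial tracking.** Suppose block position is known but each earlier allocation is known only with probability k (an assumption; the protocol gives no value). Certainty needs both matching allocations to be known, so the share is (k²/3 + k²)/4 = k²/3.

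| k | Certain share | Of 188 |
|---|---|---|
| 1 | 33.3% | 63 |
| 0.9 | 27.0% | 51 |
| 0.75 | 18.8% | 35 |
| 0.5 | 8.3% | 16 |

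**Step 5: one list shared by all centres.** Suppose patients arrive in random centre order and an observer knows the list position but sees only the own centre, of size n. Two given earlier allocations are both seen with probability (n − 1)(n − 2)/(187 × 186), and the certain share is one third of that.
- Lead centre: (107 × 106)/34,782 = 0.326; one third is 0.109; × 108 = 11.7.
- Each centre of 20: (19 × 18)/34,782 = 0.0098; one third is 0.0033; × 20 = 0.07.
- Total: 11.7 + 4 × 0.07 = 12.0 of 188 (6.4%), nearly all at the lead centre.

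**Step 6: blocks of 4 and 6 in random order, within centre.** A fully tracking observer was simulated.
- Only the sizes known: 6.3% certain at n = 20 and 5.2% at n = 108, so 80 × 0.063 + 108 × 0.052 = 10.7, about 11 of 188 (about 6%).
- Mix and quota also known: 13.3% and 6.4%, so 80 × 0.133 + 108 × 0.064 = 17.6, about 18 of 188 (about 9%).
- Best guess: about 69%.

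**The case against.** The arithmetic is not in dispute; the weight given to it is.

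- **Guessing is almost unchanged.** Someone who steers enrolment does not need certainty. The best-guess rate falls only from 70.8% to about 69.4%, so the excess over chance goes from 20.8 to 19.4 points, a relative cut of about 7%. This stands. The change removes most certain allocations and does little against guessing. Certainty is still the strongest form of foreknowledge, and removing most of it is cheap.
- **One third is an upper case.** It needs full tracking and completed within-centre blocks. This also stands, and the partial-tracking and shared-list figures show how far it can fall.
- **The list structure is not settled.** The sequence comes from the lead unit, and the rule for a short centre could point to one common list. Labels by centre and allocation in order of reception at the sub-centre make separate lists the better reading. The quotas alone are weak evidence for fixed 4s, because mixed blocks of 4 and 6 meet them too.
- **If the block of 4 is really a minimum**, sizes vary and the one-third figure does not apply. Section III.1.1 is the explicit statement and says fixed, but the two sections need reconciling.
- **The stated purpose may be modest.** It may mean only that the order should not follow a repeating pattern, which random ordering does achieve. That is a fair reading, so softening the sentence is enough.
- **Safeguards exist and small blocks protect balance.** Central generation, opaque envelopes, opening after consent and written criteria all limit misuse, and a block of 4 is a valid, common choice. None of these prevents deduction from earlier allocations, and the loss of balance under varying sizes is small.

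**Conclusion.** The concern holds. With a disclosed fixed 2:2 block of 4, full tracking and blocks completed within centre, one third of assignments are known in advance: about 63 of 188, with a 5th to 95th percentile of 57 to 68. If half of the earlier allocations are known, the figure is 16 of 188; if one list is shared by all centres, it is about 12. The protocol's description of random ordering as a means to prevent prediction therefore promises more than the scheme delivers.

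This is an avoidable weakness that should be corrected, not evidence of bias. Confidence is medium, because tracking is inferred, the list structure is not stated outright, and no effect on the primary endpoint can be derived from the protocol.

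**What to change.** **Change**
- Give each centre its own list of permuted blocks of randomly varying size, generated by the lead-unit statistician and constrained to the quotas. As an illustration with 4 and 6: two 4s and two 6s in random order make 20, and twelve 4s and ten 6s make 48 + 60 = 108.
- Keep the sizes actually used and their mix out of the protocol and all site documents.
- State in III.1.1 that each centre has its own list, and clarify the rule for a centre with fewer than four cases.
- Delete or soften the statement that ordering prevents prediction.
- Reconcile the fixed block in III.1.1 with the minimum block in III.3.

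**If enrolment has begun** (the protocol does not show trial status), change only unused envelopes after a centre's current block, and only where the remaining places allow varied sizes. With the same illustrative sizes, 16 places can be 4 + 6 + 6 in random order, 12 can be 6 + 6 or 4 + 4 + 4 drawn at random, and larger numbers allow more. With 4 or 8 places left only 4s fit, so leave those centres as they are.

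**Cost.** The list and envelopes are regenerated and two sections edited. If a centre stops mid-block, its imbalance can reach 3 instead of 2, at worst 5 × 3 = 15 instead of 5 × 2 = 10 over the five centres.

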## **3. Data management**

Use a unified EDC system (e.g., REDCap, Medidata) to set up logical checks (e.g., numerical ranges, required items).

Real-time monitoring of data entry progress and quality.

Data verification and cleanup:

Centralized data monitoring: periodic sampling of data and source documents (Source Data Verification, SDV).

Abnormal value automatic alarm (such as laboratory indicators beyond the normal range).

Central Laboratory and Imaging Center:

Biological samples are sent to the central laboratory for testing to avoid differences in testing between different laboratories.

The images were evaluated by an independent central laboratory in a blind manner.

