## **4. Monitoring and auditing (Monitoring & Auditing)**

Centralized monitoring: An independent monitoring team will check the

implementation of each center on a regular basis (frequency: once a month in the initial stage and once a quarter later).

Key inspection: subject informed consent, consistency of original data with eCRF, adverse event records.

Risk-based monitoring (RBM): Strengthen monitoring of high-risk centers or critical data points (e.g., primary endpoints).

Third-party audit: Invite an independent audit team to conduct surprise inspection on randomly selected centers to ensure compliance.

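### Envelope allocation at the sites is described as untraceable and needs no dated opening record, so an envelope opened early for a chosen patient may go unnoticed

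*Protocol*

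**What the plan says.** Section III.1.1 of the protocol sets out the allocation procedure:

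- **Sequence.** "The random sequence is generated uniformly by the statisticians of the leading unit", in SAS 9.4, at a 1:1 ratio and in fixed blocks of four.
- **Concealment.** "The random results are sealed in an opaque envelope, which only indicates the research center and the subject enrollment number".
- **Opening.** "After signing the informed consent form, the independent research assistant of the sub-center unpacks the envelope to carry out the grouping".
- **Order.** "The groups were assigned according to the order of case reception in the sub-center".
- **Stated result.** The procedure is credited with "ensuring that the assignment process is irreversible and cannot be traced back".

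The section does not ask for a date, time or signature at opening, for used envelopes to be kept, or for them to be reconciled with the statisticians' list. It does not say when an enrolment number becomes attached to a patient.

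Section 1.2 (Blinding) names only patients as blinded. Under Quality control, section V.3 (Data management) says: "Use a unified EDC system (e.g., REDCap, Medidata) to set up logical checks". Section V.4 (Monitoring and auditing) gives this list: "Key inspection: subject informed consent, consistency of original data with eCRF, adverse event records". Allocation is not on it.

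**The concern.** Concealment and traceability are different properties, and an envelope scheme needs both. Before opening, nobody at the site should be able to learn the next arm. After opening, a monitor should be able to show who opened which envelope, when, and for which patient already in the trial. Section III.1.1 provides for the first and presents the absence of the second as a merit.

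The operating team necessarily knows the anastomosis it performs. If someone learns the next arm before the next patient is committed, that patient can be approached, postponed or passed over to suit the arm. The groups then differ at baseline in ways that analysis cannot reliably repair, and the primary comparison of stool formation time carries that difference. A dated record of opening after registration lets the sponsor show that this did not happen. The protocol requires no such record.

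**Working it through.** The protocol gives no figure to reproduce on this point. The check is to take each way the scheme could fail and ask whether the records the protocol describes would show it.

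| What goes wrong | Records described | Would it show? |
|---|---|---|
| A patient receives an arm other than the one listed for that enrolment number | Central sequence; number on the envelope; source data verification | Yes, if the central list is kept and compared (the protocol states neither) |
| Envelopes are used out of numerical order | Order-of-reception rule; consent documents | Possibly, by setting enrolment numbers against consent dates; no such check is listed |
| An envelope is opened or read early, then used for a patient chosen to fit the arm | The same | Not from these records: number and arm agree with the list, and the numerical order can be intact |

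The third row is the gap. The envelope carries the number, so comparing arm with number tests whether the list was followed. It does not test whether the arm was known before the patient was committed. That needs two dated events for each patient, registration and opening, in that order. Section III.1.1 states the order through the consent rule but does not require the opening to be dated.

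Consent is also a weaker anchor than registration with confirmed eligibility. In the Screening period section, consent is item 2, while imaging and laboratory tests are items 8 and 9. The list begins with a review of eligibility and may not be chronological, but nothing says that eligibility is final before the envelope is opened.

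**Context: how much early knowledge could be worth.** With fixed blocks of four and two patients per arm, there are 6 possible orders. Assume that blocks run within centre and that someone at the site knows every earlier assignment in the block.

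- Assignments fully determined by earlier ones: 2 in each of AABB and BBAA, and 1 in each of the other four orders. The mean is (2×2 + 4×1)/6 = 8/6 = 1.33 per block, or 33.3%. Over 188 patients this is 188 × 1/3 ≈ 63.
- Chance that the best guess is right, by position: 1/2, 2/3, 2/3, 1. The mean is 2.833/4 = 70.8%, against 50% with no knowledge.

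So part of the sequence can be inferred under these assumptions even without opening an envelope early. Early opening would raise the 70.8% to 100%. These figures show why order and timing deserve a check. They do not measure bias.

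**The case against.** The case for the plan is substantial.

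1. **The scheme has real safeguards.** The envelopes are sealed, opaque and labelled with centre and enrolment number. The sequence comes from the lead unit, use follows reception order, and an independent assistant opens only after consent. A reader might infer from the phrase about tracing that no irregularity could ever be detected, or that no assignment could be verified. The documents do not support that. An arm that disagrees with the central list could be found, and the protocol does not say that the list is discarded.
2. **Oversight is wider than the key inspection list.** Section V.3 provides source data verification. Section V.4 provides an independent monitoring team, risk-based monitoring of critical data points and unannounced third-party audits. Section V.1 refers to SOPs and an operation manual that are not shown. A reader might infer that monitors and auditors would be powerless. That also goes too far, since the list of key items does not limit what they may examine.
3. **The wording may be a translation.** Paired with irreversibility, the phrase may only mean that an assignment cannot be altered afterwards. The protocol has other signs of translation.

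Points 1 and 2 stand against any absolute claim. They do not close the third row of the table: source verification needs a source, and the protocol does not require a dated opening record. An SOP might, but the protocol as written points the other way. Point 3 is plausible and would make the sentence harmless in intent. It would still need rewording, and the missing record would remain.

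**Conclusion.** The point holds in a limited form. The protocol describes allocation as untraceable and requires no dated record linking each envelope opening to a patient already registered. A wrong arm could be found if the central list is kept. An envelope opened early and then matched to a chosen patient may go undetected.

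The procedure covers all 188 planned assignments at five centres. How many might be affected, and by how much the primary comparison might move, cannot be derived from the documents, so no size of bias is claimed. Nothing in the protocol suggests that steering is expected or has occurred. The conclusion rests on section III.1.1 being the full description of allocation. If an SOP already requires dated opening records and reconciliation, what remains is to correct the wording and refer to that SOP. Otherwise the procedure should be changed, because allocation integrity is difficult to demonstrate later if it was not recorded at the time.

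**What to change.** 1. Delete the words about tracing in section III.1.1. State that an assignment cannot be changed once made and that every assignment is fully auditable.
2. Preferably, allocate through the unified EDC system planned in section V.3, releasing the arm only after the patient is registered and eligibility is confirmed. A system time stamp does not depend on the person doing the allocation.
3. If envelopes stay, use them strictly in sequence. Record the enrolment number, date, time and signature before opening, keep the used envelopes, and reconcile them with the lead statisticians' list.
4. Add allocation order to the key inspection items in section V.4.

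The cost is a randomisation set-up in the EDC system or a paper log, plus time for reconciliation. With EDC allocation, sites need system access when the patient is allocated. The sponsor should confirm that the chosen system can do this, since section V.3 names systems only as examples and for logical checks. None of these steps removes the predictability that comes from fixed blocks of four, which is a separate matter.
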